pre-vaccination and post-vaccination GMTs reported in the subjects who had received ZyVac® TCV were comparable to the respective GMTs reported in the subjects who had received the comparator TCV in this study [35].

Research Design and Methods

Describe the research design and methods and procedures to be used in achieving the specific aims of the research project. If applicable, mention the type of personal protective equipment (PPE), use of aerosol confinement, and the need for the use BSL2 or BSL3 laboratory for different part of the intended research in the methods. Define the study population with inclusion and exclusion criteria, the sampling design, list the important outcome and exposure variables, describe the data collection methods/tools, and include any follow-up plans if applicable. Justify the scientific validity of the methodological approach (biomedical, social, gender, or environmental).

Also, discuss the limitations and difficulties of the proposed procedures and sufficiently justify the use of them.

Study design

This will be a phase III effectiveness study of the typhoid conjugate vaccine (Vi-TCV) (ZyVac® TCV). The study will be conducted in a closed cohort population of children aged 6 months to 15 years residing in a selected geographical catchment area in Dhaka, Bangladesh using a test-negative design (TND). The TND is a particular type of case-control study including controls who present themselves with similar signs and symptoms (to those of the cases) in the same healthcare facilities. Individuals with the disease of interest are tested with a laboratory assay where test-positive and test-negative individuals are considered cases and controls, respectively.

Study area

The study will be conducted in wards 5, 6, 7, 48, 49, 50, 63, 71, and 72 of Dhaka South City Corporation, covering an area of ~ 10.33 km². No TCV campaigns have been conducted in this area. According to the Population and Housing Census 2022, the total population within the selected geographical catchment area is $\sim 465,000$ with households of $\sim 122,000$. The proportion of males is 54 percent and the average household size is ~ 3.8 people. Assuming $\sim 20\%$ of the population is from the 6-month to 15-year age group, the expected number of age-eligible children is $\sim 92,000$.

Baseline mapping

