All the households that have age-eligible children will be informed to visit the nearest vaccination centre. If a participant's birth certificate or national immunization cards were not provided during the baseline listing, we will notify their parents or guardians to bring them during vaccination. After arrival at the vaccination centre, the participant and vaccination ID will be verified with the listing database and the master list. Then the screening will be carried out according to inclusion/exclusion criteria.

Informed consent

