Surveillance for enteric fever will be undertaken at the Maniknagar field office and Mugda Medical College and Hospital for all age-eligible (from 6 months to 15 years) residents recorded in the baseline list. Participants with a subjective history of ≥2 days of fever and/or a temperature of ≥38°C at presentation will be enrolled in the surveillance. A blood sample (3ml) will be collected for microbiological culture. The participants will receive appropriate clinical management. Blood culture-positive patients will be visited at home to confirm their identity, and collect information about their illness and patients will be asked to visit the field office if their condition is not improved. The treatment will be adjusted as necessary, based on laboratory testing.

Study staff will visit households, included in the baseline listing, periodically, to remind them to seek treatment at the Maniknagar field office if their children (both vaccinees and non-vaccinees) develop a fever.

Eligibility criteria for enrollment in the passive surveillance

- Participants information, available in the listing database
- Parent/guardian is willing and competent to provide informed consent. For participants aged 11 to 15 years, informed assent will also be considered
- Participants from the study area who experienced a fever lasting for ≥2 days and/or temperature ≥38°C at presentation [4, 30]
- Participants aged 6 months to 15 years on the first day of the vaccination campaign

Flow diagram

Laboratory procedures

Passive surveillance samples

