SOP and training																						
materials																						
development																						
Training for																						
vaccination and																						
surveillance																						
Listing of																						
interested children																						
for vaccination in																						
the study area																						
Vaccination																						
AEFI recording																						
SAE recording																						
and reporting																						
Diary card review																						
Patient enrollment																						
in the passive																						
surveillance																						
Patient																						
management																						
Sample collection																						
for imunogenicity																						
and passive																						
surveillance																						
Laboratory																						
analysis																						
Data cleaning																						
Development of																						
statistical analysis																						
plan																						
Data analysis																						
Clinical study																						
report (CSR)																						
development																						
Manuscript																						
writing and																						
submission																						
Dissemination of																						
findings in																						
national and																						
	 	1	1	 	 	l	l	l	1									1	1	1		

international											
community											

Sample Size Calculation and Outcome (Primary and Secondary) Variable(s)

Clearly mention your assumptions. List the power and precision desired. Describe the optimal conditions to attain the sample size. Justify the sample size that is deemed sufficient to achieve the specific aims.

A sample size of 515 (103 cases and 412 controls) will be required in this case-control test-negative design study assuming vaccine effectiveness of 80%, vaccine coverage of 65% in the target age-eligible population (6 months to 15 years), 4 controls per case, precision width of \pm 10% (20%) and type 1 error rate of 0.05. Considering the incidence rate for typhoid fever of 230 per 100,000 person-years among the non-vaccinated population aged 6 months to 15 years, the target number of vaccinations is \sim 60,000.

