To achieve the target number of vaccinees aged 6 months to 15 years representing \sim 31% of the total population), the required age-eligible children and population of all age groups will be \sim 92,000 and \sim 297,000 respectively.

Data Analysis

Describe plans for data analysis, including stratification by sex, gender and diversity. Indicate whether data will be analysed by the investigators themselves or by other professionals. Specify what statistical software packages will be used and if the study is blinded, when the code will be opened. For clinical trials, indicate if interim data analysis will be required to determine further course of the study.

Focal time

Focal time will be defined as the date of onset of symptoms leading to presentation for care.

Culture-positive case

Eligible febrile patients who will be positive by blood culture for *Salmonella enterica* serotype Typhi and symptoms developed >14 days after vaccination, or, if unvaccinated, >14 days after the midpoint of the vaccination period.

Culture-negative control

Eligible febrile patients who will be negative by blood culture for *Salmonella enterica* serotype Typhi and symptoms developed >14 days after vaccination, or, if unvaccinated, >14 days after the midpoint of the vaccination period. Given that the sensitivity of the blood culture method is ~59% [36], we will apply the clinical rule, defined in a previous analysis for blood culture-negative typhoid patients, to exclude clinical typhoid patients from the analysis [37]. This exclusion will be helpful for a better evaluation of the magnitude of protection conferred by the vaccine in the proposed study.

Matching of cases and controls

A statistician, blinded to the vaccination status of participants will select blood culture-negative controls (after excluding clinical typhoid patients, vide supra) against each case. Matching of controls for each case will then be done considering the age groups at focal time (6 months to <2 years; 2 to 4 years; and 5 to 15 years) and date of presentation. Controls will be randomly selected on the day of the presentation; if matched controls will not be available on that day, the selection period will be widened for up to a maximum of ± 7 days.

Statistical analysis

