For the evaluation of vaccine protection, a conditional logistic regression model will be used, considering matched case-control status as the outcome and vaccination status and selected covariates as independent variables, taking non-receipt of vaccine as the referent category for assessment of vaccine protection. Odds ratios for the associations between vaccination and typhoid fever will be estimated by exponentiation of the coefficient for vaccination from the fitted model, and the standard error of the coefficient will be used to calculate 95% confidence intervals for the estimated effect. Protective effectiveness will be calculated as $[(1 - \text{odds ratio}) \times 100\%]$. The threshold of statistical significance will be considered at P < 0.05.

Analysis of immunogenicity and safety data

Geometric Mean Titres (GMT) and seroconversion rate (≥4-fold rise of anti-Vi-IgG antibody titre induced on day 30 compared to day 0 before vaccination) of anti-Vi-IgG antibody titre will be calculated. Analysis of covariance will be used to adjust for imbalances in baseline titres.

In addition, descriptive analyses of safety data will be done for AEFI or SAEs cases.

Shell table for effectiveness of the typhoid conjugate vaccine against culture-confirmed typhoid cases

	Typhoid C	Cases	Matched c	ontrols	Vaccine effectiveness (VE) (95% CI)					
Overall period	Vaccinees n/N (%)	Non- vaccinees n/N (%)	Vaccinees n/N (%)	Non- vaccinees n/N (%)	Crude VE	P value	Adjusted VE	P value		
All ages	 	I	 	I	 	 		 		
6 months - <2 years										
2 - 4 years										
5 - 15 years										
First six months										
All ages										
Second six mont	hs									
All ages										

Data Safety Monitoring Plan (DSMP)

All clinical investigations (research protocols testing biomedical and/or behavioural intervention(s)) should include the Data and Safety Monitoring Plan (DSMP). The purpose of DSMP is to provide a framework for appropriate oversight and monitoring of the conduct of clinical trials to ensure the safety of participants and the validity and integrity of the data. It involves involvement of all investigators in periodic assessments of data quality and timeliness, participant recruitment, accrual and retention, participant risk versus benefit, performance of trial sites, and other factors that can affect study outcome.

Trial Monitoring

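### Does matching controls on age group and date, but not on enrolling facility, bias the primary vaccine effectiveness?

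*Protocol*

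**What the plan says.** Under Data Analysis, Matching of cases and controls, the rule is: "Matching of controls for each case will then be done considering the age groups at focal time", together with date of presentation. "Controls will be randomly selected on the day of the presentation", with the window widened to at most 7 days either side if no matched control is available. A statistician blinded to vaccination status makes the selection.

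Under Surveillance for enteric fever there are two enrolling sites: "Surveillance for enteric fever will be undertaken at the Maniknagar field office and Mugda Medical College and Hospital". Staff visit listed households periodically "to remind them to seek treatment at the Maniknagar field office if their children (both vaccinees and non-vaccinees) develop a fever".

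Vaccination is by invitation (Verification of the potentially eligible children): "All the households that have age-eligible children will be informed to visit the nearest vaccination centre". The Sample Size Calculation assumes "vaccine coverage of 65% in the target age-eligible population".

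The Statistical analysis section specifies conditional logistic regression with "vaccination status and selected covariates as independent variables", and its shell table has separate columns for crude and adjusted effectiveness. The Study design section describes test-negative controls in general as "controls who present themselves with similar signs and symptoms (to those of the cases) in the same healthcare facilities".

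**The concern.** Vaccination is not randomised, so the primary odds ratio is only as good as the comparability of cases and controls. A field office and a teaching hospital are unlike places, and households are steered to one of them. Families who use the hospital anyway may live elsewhere or respond less to study contact, and the same traits could govern whether they came for vaccination. Facility would then be a recorded, partial marker of a confounder that the selection rule ignores. A resulting bias would be systematic, so more cases would not remove it, and it would fall on the sole primary objective. The Study design wording about the same healthcare facilities can also be read as a promise that the matching rule does not keep.

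**Working it through.** **1. The planned precision, for scale.** Inputs from the Sample Size Calculation: effectiveness 80% (OR 0.20), coverage 65%, 4 controls per case, full 95% interval width 20 points.

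- Coverage in cases = 0.2×0.65 / (0.35 + 0.2×0.65) = 0.2708.
- Variance of log OR, per case: V = 1/(0.2708×0.7292) + 1/(4×0.65×0.35) = 6.163.
- Solving 0.20×(e^{1.96s} − e^{−1.96s}) = 0.20 for s gives n = V/s² = 102.2, so 103 cases and 412 controls. This reproduces the protocol's 515.
- At 103 cases, s = 0.2446 and the interval around 80% is 67.7% to 87.6%.

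**2. When does ignoring facility bias the estimate?** All site-specific inputs here are assumptions; the protocol gives none. Take two sites with a true OR of 0.20 in each. A share w of controls is at site B, the coverages are c_A and c_B with mean 65%, and k is the ratio of baseline typhoid-to-control odds at B relative to A. Then

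OR = {0.2[(1−w)c_A + w·k·c_B] / [(1−w)(1−c_A) + w·k·(1−c_B)]} / (0.65/0.35).

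- With k = 1 the braces reduce to 0.2×0.65/0.35, so effectiveness is 80.0% at every coverage gap. A link between uptake and site choice is not enough on its own.
- With k = 2, w = 0.35, c_A = 0.72 and c_B = 0.52: 0.1664/0.518 = 0.3212, and 0.3212/1.857 = 0.173, so effectiveness reads 82.7%.
- Over w from 0.20 to 0.50, k = 2 with gaps of 10 to 20 points gives 76.7% to 82.7%. The extreme corner (k = 5, 30-point gap) gives 65.2% to 87.5%.

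**3. How much would using facility recover?** In step 2 site is the whole confounder, so adjusting for it restores 80.0% by construction. A more realistic model makes facility a partial marker. Assume 75% of children are in families engaged with the field office and 25% are not, with hospital use of 5% and 80% respectively. In the first four rows attendance (engaged/other) is 60%/30% for other fevers and 80%/70% for typhoid. In the last two it is 40%/70% for other fevers and 80% in both groups for typhoid. True effectiveness is 80%.

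| Coverage, engaged/other | Without facility | With facility | Gain (points) |
|---|---|---|---|
| 67/59 | 80.6% | 80.3% | 0.3 |
| 70/50 | 81.4% | 80.7% | 0.7 |
| 75/35 | 82.8% | 81.3% | 1.5 |
| 75/35, typhoid twice as common in the other group | 86.6% | 83.4% | 3.2 |
| 70/50, attendance reversed | 77.8% | 79.1% | 1.3 |
| 75/35, attendance reversed | 75.5% | 78.1% | 2.6 |

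For 70/50, unreversed, without facility: the vaccination odds are 0.3525/0.1725 = 2.0435 in controls and 0.1015/0.2675 = 0.3794 in cases, so OR = 0.1857. The with-facility column comes from logistic regression on the expected counts with a facility term. If the typhoid-to-other-fever attendance ratio is equal in the two groups (say 80%/40% for typhoid against 60%/30% for other fevers), the 75/35 gap gives exactly 80.0% with or without facility.

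**4. What can using facility cost?** Suppose there is no shared cause, but typhoid makes hospital attendance more likely and vaccination makes it less likely. Assume a 30% baseline hospital share, hospital odds ×3 for cases and ×0.5 for vaccinees.

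- The probability of attending the field office is 0.7000 for unvaccinated controls, 0.8235 for vaccinated controls, 0.4375 for unvaccinated cases and 0.6087 for vaccinated cases.
- Without facility, OR = 0.20 and effectiveness is 80.0%, which is correct.
- Within the field office, OR = 0.20 × (0.6087×0.7000)/(0.4375×0.8235) = 0.2365. The hospital stratum gives the same value. Effectiveness reads 76.3%, a loss of 3.7 points.
- With milder inputs (×2 and ×0.7) the factor is 1.056 and effectiveness reads 78.9%, a loss of 1.1 points.

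The 3.7-point loss exceeds every gain in step 3. The milder 1.1-point loss exceeds the gains in the first two rows.

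**5. Is that second structure plausible here?** Yes. Under Adverse events follow up, vaccinees' parents outside the 600-child subset are encouraged to use the adverse event cell at the Maniknagar field office, and subset families are told to attend that office for fever. Vaccination may therefore itself move families towards the field office. The household reminders to vaccinated and unvaccinated families alike work against this, but need not cancel it.

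**6. Does the rule shut out adjustment?** No. Facility is not a matching factor, so it varies within matched sets and can be a covariate in the conditional model. Baseline listing also records address and a GIS identifier, which measure residence more directly than facility does.

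**The case for a change.** The strongest case for acting is that the selection rule is fixed in the protocol, so a later analysis plan can adjust for facility but cannot make the sets facility-matched without amending the rule. Settling the role of facility before vaccination status is linked would also prevent a result-driven choice of adjustment. The cost is small: if facility matching cut the average to 3 controls per case, the interval would widen from 19.9 to 20.5 points, and the covariate route loses no controls at all.

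Most of this is true, but it does not make the rule wrong. Same-facility selection is a trade-off that helps under one causal structure and harms under another, and the protocol gives no figures to decide between them. Prespecifying the covariates is sound practice, but it belongs in the statistical analysis plan, which the Study timeline lists as a separate item and which is not at hand. The Study design wording does not tip the balance either: it describes test-negative studies in general and is met when cases and controls come from the same two facilities.

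**Conclusion.** The concern does not hold. Matching on age group and date is not shown to give a wrong answer, and it contradicts nothing else in the protocol. The assumed shifts of roughly 1 to 7 points rest on coverage gaps of 8 to 40 points, on unequal typhoid-to-other-fever ratios, and on no adjustment for facility or residence, although the protocol provides for an adjusted estimate. The top figure, 86.6%, needs the 40-point gap together with a 3.5-fold difference in that ratio (0.70/0.30 against 0.80/0.60 is 1.75-fold, then doubled). Against this, facility recovers 0.3 to 3.2 points in those scenarios and costs 1.1 to 3.7 points where vaccination and illness affect site choice. Reporting effectiveness with and without facility would be a reasonable sensitivity analysis, but that is a preference for the analysis plan and not a correction to the protocol.

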In a hypothesis testing research proposal, briefly mention the hypothesis to be tested and provide the scientific basis of the hypothesis, critically examining the observations leading to the formulation of the hypothesis.

Does this research proposal involve testing of hypothesis: \(\simega\) No \(\simega\) Yes (describe below)

The typhoid Vi-polysaccharide conjugate vaccine will be effective in preventing typhoid fever among Bangladeshi children.

Specific Objectives:

Describe the specific objectives of the proposed study. State the specific parameters, gender aspects, biological functions, rates, and processes that will be assessed by specific methods.

Primary objective:

To evaluate the effectiveness of typhoid conjugate vaccine (TCV) against blood culture-confirmed typhoid fever using the test-negative design

Secondary objective:

- To evaluate the effectiveness of typhoid conjugate vaccine (TCV) against blood culture-confirmed typhoid fever stratified by age groups (6 months to <2 years, 2 to 4 years, 5 to 15 years)
- To evaluate the effectiveness of typhoid conjugate vaccine (TCV) against blood culture-confirmed typhoid fever stratified by the period of follow-up (first and second six months) after vaccination
- To determine the immunogenicity of TCV in a subset of participants, stratified by age groups (6 months to <2 years, 2 to 4 years, 5 to 15 years)

Background of the Project including Preliminary Observations:

Provide scientific validity of the hypothesis based on background information of the proposed study and discuss previous works on the research topic, including information on sex, gender and diversity (ethnicity, SES) by citing specific references. Critically analyze available knowledge and discuss the questions and gaps in the knowledge that need to be filled to achieve the proposed aims. If there is no sufficient information on the subject, indicate the need to develop new knowledge.

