A map of the study area will be created based on open-source georeferenced satellite images (source: Esri, Maxar, Earthstar Geographics, and the GIS User Community). The satellite image of the study area will be printed by separating it into several small pieces and provided to the field team for data collection. In this process field team will visit the entire area according to the map and draw the structure/building, road, and other salient geographic features in the printed images. A unique geographical information system (GIS) identification number will be assigned for all the buildings/structures, and submitted to the GIS team to develop the digital vector data (point, line, and polygon feature). The digital data of structure/building (polygon feature) centroid x and y coordinates will be used to represent real-world coordinate values or GPS values.

[figure not shown]

Figure: Study catchment area with health facilities

Baseline listing

All households in the study area will be assigned a unique identification number and all household members will be enumerated. Information about the age-eligible children including name, age, sex, date of birth, and parent's name will be obtained. In addition, the name of the HH head, address, and cell phone number of HHs will be collected. The previously assigned GIS ID will be incorporated into the baseline listing form and the newly identified structure will be updated in the GIS database. We will take photos of birth certificates or national immunization cards to confirm the age of participants if available. Verbal consent will be provided by either the head of the household or a key informant.

Participant card for potentially eligible children for vaccination

After preparing the baseline list, we will identify the age-eligible (6 months to 15 years) participants. Then we will prepare participant cards for all eligible children which will be provided before the vaccination. There will be a unique identification number on the participant card which will be used during vaccination. A master list of potential eligible participants will be prepared.

Vaccination

Inclusion criteria for vaccination:

The participant must satisfy all the following criteria to be eligible for enrolment:

- Participant was included in the baseline list of the study population
- Participants living within the study catchment area at the time of vaccination

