- Parent/guardian is willing and competent to provide informed consent (if the participant is 11 to 15 years of age, assent will also be sought)
- Participants aged between 6 months to 15 years (i.e. up to 15 years 364 days) at the time of vaccination
- Apparently healthy (no complaints of febrile illness) on the day of vaccination
- Parent/guardian confirms that their child will be willing and be able to comply with study requirements

Exclusion criteria for vaccination:

The participant will not be enrolled if any of the following criteria apply:

- Has knowingly received a typhoid vaccine in the past
- Known allergy to any vaccine in the past
- Medical or social reasons that will prevent the participant from conforming to the study requirements as judged by a medical professional
- Planning to move away from the catchment area within the next 12 months
- Pregnant at the time of vaccination, as confirmed by a urine test (urine pregnancy test will be done in girls who are married)
- Confirmed or suspected immunosuppressive or immunodeficiency disorder; or subjects on any immunosuppressive or immunostimulant therapy
- Subject participated in another clinical study in the past 3 months

Temporary exclusion criteria for vaccination:

Participants will be temporarily excluded from being vaccinated if, at the point of vaccination, any of the following apply:

- Receipt of any other vaccines in the last 30 days
- Current temperature of at least 38°C or reported fever within 24 hours prior to vaccination
- Use of antipyretics within 4 hours prior to vaccination
- Unmarried girls between the ages of ≥12 to 15 years old whose first day of their last menstrual period (LMP) is more than 28 days ago or who do not know the date they last menstruated upon presentation

If these apply, the participant will be temporarily excluded from vaccination until the temporary exclusion criteria no longer apply. Please note, for children with fever above 38° C this must be a minimum of 48 hours after the fever has resolved. Unmarried girls between the ages of ≥ 12 to 15 years whose first day of their LMP is more than 28 days or who do not know the date they last menstruated upon presentation will be asked to return after starting their next

menstruation for vaccination. A re-assessment will be conducted to ensure these temporary exclusion criteria no longer exist.

Verification of the potentially eligible children

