A DSMB will also be formed to oversee the safety component of the study. The DSMB members will not be involved in the study in any way. In addition, a physician with relevant study-related or therapeutic expertise will be identified as an independent safety monitor (ISM). The ISM will not be an investigator for this study. Under any circumstances, the identified ISM would be requested to carry out an independent assessment of the child presented with adverse events. The assessment details will be reported to the PI and DSMB.

Pregnancy follow-up

Follow-up on pregnancy outcomes will be conducted for all married girls identified during routine follow-up as either being pregnant at the time of vaccination or becoming pregnant within three months of vaccination. This follow-up will include monthly visits until the end of the pregnancy, with the final contact occurring after delivery or pregnancy outcome. Starting from the eighth month of gestation, additional weekly follow-ups will be conducted via phone calls. We will record pregnancy-related information considering it as a medically important event.

Immunogenicity study

A subset of 600 participants will be enrolled in the immunogenicity sub-study and will have an additional three face-to-face follow-up visits at the field office at one month (D30/+7 days), at 6 months (D180+/-14 days), and at one year (D365+/-30 days) after vaccination. The first 200 participants from each age stratum (6 months to <2 years, 2 to 4 years, 5 to 15 years) who give their consent will be selected and enrolled for the immunogenicity sub-study.

At these additional visits, the following procedures will be performed:

- Confirmation of continued participation in the study
- Collection of blood (3ml for 6 months to 4 years and 5ml for 5 to 15 years)
- Confirmation of contact details and reiteration of instructions to attend the health care facilities in case of fever for ≥2 days and/or temperature ≥38°C at presentation.

The above information will be recorded in the immunogenicity CRF. Parents/guardians of participants enrolled in the immunogenicity study will be given details of the follow-up appointments.

Surveillance for enteric fever

[figure not shown]

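### Do children who turn 16 during follow-up fall outside the matching age bands and so out of the primary analysis?

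*Protocol*

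**What the plan says.** Three rules in the protocol meet here.

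- **Eligibility.** The criteria for enrollment in the passive surveillance require "Participants aged 6 months to 15 years on the first day of the vaccination campaign". Age is read once, on a fixed calendar day, and no upper age at presentation is given.
- **Matching.** Under Matching of cases and controls, controls are chosen "considering the age groups at focal time (6 months to <2 years; 2 to 4 years; and 5 to 15 years") and by date of presentation. The Focal time paragraph sets that time at symptom onset, so this is attained age. The shell table for effectiveness uses the same three age rows, plus rows for all ages.
- **Meaning of the upper limit.** The inclusion criteria for vaccination read "Participants aged between 6 months to 15 years (i.e. up to 15 years 364 days) at the time of vaccination". A child aged 16 at onset is therefore outside the top band if its label is taken literally.

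Under Statistical analysis, "a conditional logistic regression model will be used, considering matched case-control status as the outcome". The secondary objectives ask for effectiveness "stratified by the period of follow-up (first and second six months) after vaccination".

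**The concern.** The cohort is closed and its members age. A child aged 15 on the first campaign day can have culture-confirmed typhoid at 16, be eligible under the surveillance rule, and still have no stated matching band. A case with no matched control drops out of a conditional likelihood. If such cases were dropped, eligible primary-outcome events would be lost in a study whose own inputs yield almost exactly the number it needs. The loss would also grow with time, so it would fall mainly on the second six-month period, which is a named secondary comparison.

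**Working it through.** **Inputs.** From the sample size section: effectiveness 80% (odds ratio 0.20), coverage 65%, 4 controls per case, total interval width 20 points, and "Considering the incidence rate for typhoid fever of 230 per 100,000 person-years among the non-vaccinated population". From the project summary: about 92,000 eligible children, about 60,000 of them vaccinated, so 32,000 unvaccinated. Assumed, because the protocol does not give them: ages uniform from 6 months to just under 16 years (a span of 15.5 years), flat incidence by age, and 12 months of follow-up.

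**The plan's figure.**
- Vaccinated share among cases: 0.65×0.2 / (0.65×0.2 + 0.35) = 0.2708.
- V = 1/(0.2708×0.7292) + 1/(4×0.65×0.35) = 6.163.
- Interval width = 2×0.2×sinh(1.96×√(V/n)). Setting this to 0.20 gives n = 102.2, rounded up to 103 cases and 412 controls. The stated size is reproduced.

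**Expected cases.** (32,000 + 60,000×0.2)×230/100,000 = 101.2 in 12 months. Removing the first 14 days: 101.2×351/365 = 97.3.

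**Share of follow-up at age 16.** Children aged 15 on day 1 are 1/15.5 = 6.45% of the cohort.
- Counting from day 1, they spend on average half the year at 16: 0.5/15.5 = 3.2%.
- Counting from day 14, the mean elapsed time is (14/365 + 1)/2 = 0.519 years: 0.0645×0.519 = 3.3%.
- Counting the unvaccinated from 14 days after the campaign midpoint, as the case definition does, their share is 3.8% to 5.1% for an assumed campaign of 1 to 6 months.

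**Cases affected on the literal reading.** 97.3×0.0335 = 3.3. If 15-year-olds are a share s = 4% to 8% of the cohort with relative incidence r = 0.5 to 1, the loss is s·r/(s·r + 1 − s)×0.519 = 1.06% to 4.15%, or 1.0 to 4.0 cases. The Background puts peak incidence at 5 to 9 years, which favours the lower part of this range.

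**Effect on precision at 80% effectiveness.**

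| Start of count | Cases, none lost | Width | Cases, literal reading | Width |
|---|---|---|---|---|
| Day 1 | 101.2 | 20.1 | 97.9 | 20.5 |
| Day 14 | 97.3 | 20.5 | about 94 | 20.9 |

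Either way the interval widens by 0.4 points.

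**By period.** First six months: mean elapsed time (14/365 + 0.5)/2 = 0.269, and 0.269/15.5 = 1.7%. Second six months: 0.75/15.5 = 4.8%. About 75% of the loss falls in the second period. Losing 4.8% of cases there multiplies the standard error by about √(1/0.952) = 1.025.

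**Bias.** The rule would remove cases and controls by age at onset, not by vaccination status. The other matched sets are untouched, so the odds ratio among those under 16 is not distorted.

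**The case for a change.** The strongest argument for a change is that this is more than detail left to the analysis plan. The protocol itself fixes the eligibility date, the date at which age is read for matching, and the bands, and these do not fit together. The expected case count has no surplus over 103, and one clause would settle the matter. What stands of this is that the placement of a 16-year-old is unstated.

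The rest weakens on inspection. The loss is inferred, since no rule excludes these children. The three bands are the study's standard age labels, used in the objectives and again for the immunogenicity subset ("The first 200 participants from each age stratum (6 months to <2 years, 2 to 4 years, 5 to 15 years"), and the top one is plainly the oldest stratum. Placing a 16-year-old there breaks no rule. The baseline listing collects "Information about the age-eligible children including name, age, sex, date of birth", so age on any date can be computed and no data are lost.

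The comparison of about 94 cases with 103 overstates the matter. Of the gap of 9, 1.8 comes from the plan's rounded inputs (103 − 101.2) and 3.9 from the 14-day lag (101.2 − 97.3); only 3.3 concerns age. Controls aged 16 cost little, because controls are sampled for each case and one fewer candidate matters only if the pool runs short.

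Banding everyone by age on the first campaign day would remove the ambiguity, but it brings no clear gain. Matching on attained age is a legitimate choice, and replacing it would change what the age-specific effectiveness estimates mean.

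**Conclusion.** No change to the plan is needed. The eligibility rule and the band labels leave the placement of a child who turns 16 unstated, but analysts will fill that gap sensibly by using the oldest band, and then nothing is lost. On the least favourable reading, about 1 to 4 of roughly 100 cases could not be matched, the overall interval would widen by about 0.4 points, and the second-period standard error would rise by about 2.5%. No bias in effectiveness is shown, and the primary conclusion would stand. The sizes rest on 12 months of follow-up, inferred from the two six-month periods, and on assumed ages and incidence. A longer counted window for the unvaccinated raises the share somewhat; lower incidence in the oldest children reduces it. Neither alters the conclusion.
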